7.3 Subject Population(s) for Analysis

Our primary analysis will be performed based on the intention to treat. Therefore, any subject randomized into the study, regardless of whether they received study drug, will be included in the primary analysis. A subgroup analysis will also be performed on patients who received the allocated treatment as per the planned protocol, and patients undergoing reverse vs anatomic primary TSA.

8 Safety and Adverse Events

8.1 Definitions

Unanticipated Problems Involving Risk to Subjects or Others (UPIRTSO)

Any unanticipated problem or adverse event that meets the following three criteria:

- Serious: Serious problems or events that results in significant harm, (which may be physical, psychological, financial, social, economic, or legal) or increased risk for the subject or others (including individuals who are not research subjects). These include: (1) death; (2) life threatening adverse experience; (3) hospitalization - inpatient, new, or prolonged; (4) disability/incapacity - persistent or significant; (5) birth defect/anomaly; (6) breach of confidentiality and (7) other problems, events, or new information (i.e. publications, DSMB reports, interim findings, product labeling change) that in the opinion of the local investigator may adversely affect the rights, safety, or welfare of the subjects or others, or substantially compromise the research data, **AND**
- Unanticipated: (i.e. unexpected) problems or events are those that are not already described as potential risks in the protocol, consent document, not listed in the Investigator's Brochure, or not part of an underlying disease. A problem or event is "unanticipated" when it was unforeseeable at the time of its occurrence. A problem or event is "unanticipated" when it occurs at an increased frequency or at an increased severity than expected, **AND**
- Related: A problem or event is "related" if it is possibly related to the research procedures.

Non-UPIRTSO

A reportable event that does not meet the Mayo Clinic IRB's definition of a UPIRTSO.

Adverse Event

An untoward or undesirable experience associated with the use of a medical product (i.e. drug, device, biologic) in a patient or research subject.

Serious Adverse Event

Adverse events are classified as serious or non-serious. Serious problems/events can be well defined and include;

- death
- life threatening adverse experience
- hospitalization
- inpatient, new, or prolonged; disability/incapacity
- persistent or significant birth defect/anomaly

And/or per protocol may be problems/events that in the opinion of the sponsor-investigator may have adversely affected the rights, safety, or welfare of the subjects or others, or substantially compromised the research data.

All adverse events that do not meet any of the criteria for serious, should be regarded as **non-serious adverse events**.

Adverse Event Reporting Period

For this study, the study treatment follow-up period is defined as 7 weeks following the last administration of study treatment.

Preexisting Condition

A preexisting condition is one that is present at the start of the study. A preexisting condition may be recorded as an adverse event if the frequency, intensity, or the character of the condition worsens during the study period.

General Physical Examination Findings

At screening, any clinically significant abnormality should be recorded as a preexisting condition. Throughout the study, any new clinically significant findings/abnormalities that meet the definition of an adverse event must also be recorded and documented as an adverse event.

Adverse Event Causality

We understand the importance pharmacovigilance, and the significance of establishing a relationship between study drug and adverse events. Causality assessment or algorithms are available to assist with evaluating the likelihood or relationship between study drug and adverse event. We will utilize the WHO-UMC causality assessment system to assess adverse event causality.³⁹

Post-study Adverse Event

Unresolved adverse events related to the study medication/procedure will be followed by the PI/Co-PI's until the events are resolved, the subject is lost to follow-up, or the adverse event is otherwise explained

Hospitalization, Prolonged Hospitalization or Surgery

Any adverse event that results in hospitalization or prolonged hospitalization should be documented and reported as a serious adverse event unless specifically instructed otherwise in

this protocol. Any condition responsible for surgery should be documented as an adverse event if the condition meets the criteria for an adverse event.

- Neither the condition, hospitalization, prolonged hospitalization, nor surgery are reported as an adverse event in the following circumstances: Hospitalization or prolonged hospitalization for diagnostic or elective surgical procedures for a preexisting condition. Surgery should **not** be reported as an outcome of an adverse event if the purpose of the surgery was elective or diagnostic and the outcome was uneventful.
- Hospitalization or prolonged hospitalization for therapy of the target disease of the study, unless it is a worsening or increase in frequency of hospital admissions as judged by the clinical investigator.

8.2 Recording of Adverse Events

The study team will seek information on adverse events by specific questioning and, as appropriate, by examination. This will occur on daily follow up inpatient encounters as well as telephone or office visit encounters around 12-16 weeks post-procedure. Information on all adverse events will be recorded in the electronic medical record and also in the appropriate adverse event worksheet. Related signs, symptoms, and abnormal diagnostic, laboratory or procedure results will be recorded as well. PI/Co-PI's will be notified of the adverse events.

The clinical course of each adverse event will be followed until resolution, stabilization, or until it has been determined that the study treatment or participation is not the probable cause. Serious adverse events that are still ongoing at the end of the study period will be followed, as stated above. Any serious adverse event that occurs after the study period and is considered related to the study treatment or study participation will be recorded and reported.

8.3 Reporting of Serious Adverse Events and Unanticipated Problems

When an adverse event has been identified, the study team will take appropriated action necessary to protect the study participant and then complete the Study Adverse Event Worksheet and log. The sponsor-investigator will evaluate the event and determine the necessary follow-up and reporting required.

Serious adverse events will be evaluated and reported per institutional policy and regulatory requirements.

8.3.1 Sponsor-Investigator reporting: notifying the Mayo IRB

Information collected on the adverse event worksheet (*and entered in the research database*):

- Subject's name:
- Medical record number:
- Disease/histology (if applicable):
- The date the adverse event occurred:
- Description of the adverse event:
- Relationship of the adverse event to the research (drug, procedure, or intervention):

- If the adverse event was expected:
- If any intervention was necessary:
- Resolution: (was the incident resolved spontaneously, or after discontinuing treatment)
- Date of Resolution:

The sponsor-investigator will review all adverse event reports to determine if specific reports need to be made to the IRB and FDA. The sponsor-investigator will review the adverse event worksheet and only directly related SAEs/UPIRTSOs will be reported to the IRB.

For NON-UPIRTSOs, the investigator reports problems or events that do NOT meet the criteria of an UPIRTSO to the Mayo Clinic IRB in summary format at the time of the next continuing review.

8.3.2 Sponsor-Investigator reporting: Notifying the FDA

Any applicable IND regulations will be followed related to reporting to the FDA of all unexpected, serious suspected adverse reactions according to the required IND Safety Reporting timelines, formats and requirements.

Unexpected fatal or life threatening suspected adverse reactions where there is evidence to suggest a causal relationship between the study drug/placebo and the adverse event, will be reported as a serious suspected adverse reaction. This will be reported to the FDA on FDA Form 3500A, no later than 7 calendar days after the sponsor-investigator's initial receipt of the information about the event.

Other unexpected serious suspected adverse reactions where there is evidence to suggest a causal relationship between the study drug/placebo and the adverse event, will be reported as a serious suspected adverse reaction. This will be reported to the FDA on FDA Form 3500A, no later than 15 calendar days after the sponsor-investigator's initial receipt of the information about the event.

Any clinically important increase in the rate of serious suspected adverse reactions over those listed in the protocol or product insert will be reported as a serious suspected adverse reaction. This will be reported to the FDA on FDA Form 3500A no later than 15 calendar days after the sponsor-investigator's initial receipt of the information about the event.

Findings from other studies in human or animals that suggest a significant risk in humans exposed to the drug will be reported. This will be reported to the FDA on FDA Form 3500A, no later than 15 calendar days after the sponsor-investigators initial receipt of the information about the event.

8.4 Unmasking/Unblinding Procedures

This study is an unblinded study.

8.5 Stopping Rules

Adverse events and serious adverse events, as defined in Section 8.1 of IND protocol, will be monitored by the study team for patient safety. Known serious adverse events associated with interscalene nerve blocks (SISB and CISB groups) include inadvertent intravascular injection⁺, local anesthetic systemic toxicity (LAST)*, inadvertent epidural or subarachnoid injection, and pneumothorax. Additionally, patients will be monitored throughout the procedure utilizing standard ASA monitors, aspirating for heme or cerebral spinal fluid (CSF) prior to administration of local anesthetic solution in divided doses, frequent assessment of the patient's well-being via verbal communication, and having emergency medications and airway equipment readily available at all times. Performing this regional block is considered standard in our practice and these methods are already established procedures in the practice of perioperative pain control for a total shoulder arthroplasty.^{4,5}

Serious adverse event associated with local infiltration analgesia (LIA group) is local anesthetic systemic toxicity (LAST).

⁺ *Inadvertent intravascular injection is suspected if a patient experiences sudden loss of consciousness, apnea, convulsions, hypotension, respiratory depression, or stroke symptomology.*

^{*} *Local anesthetic systemic toxicity is suspected if a patient has acute onset of central nervous system changes (tinnitus, metallic taste in mouth, perioral numbness) or cardiovascular changes (bradycardia, hypotension, EKG changes).*

LAST is a known serious adverse event with any local anesthetic administration. Preventive measures include high degree of suspicion, vital sign monitoring (blood pressure, EKG, oxygen saturation), using an appropriate dose of local anesthetic, injecting local anesthetic in divided dose, aspirating prior to injection of medication looking for heme, consider using epinephrine in solution as a vascular marker, being prepared to treat a LAST event immediately (checklist, external defibrillator, resuscitate medications, emergency airway equipment), and having lipid emulsion therapy readily available (standard of care).⁴⁶ We acknowledge that despite the rarity of these serious adverse events, the potential still exists.

Study stopping criteria includes:

CISB and SISB groups:

- a) The study will stop if 5% of subjects in either group experience inadvertent intravascular injection, inadvertent epidural or subarachnoid injection, and pneumothorax.
- b) The study will stop if 5% of subjects in either group experience LAST.

LIA group

- a) The study will stop if 5% of subjects experience LAST.

We acknowledge that unanticipated adverse events may arise during this study.

CISB, SISB, and LIA groups:

- a) The study will stop if 5% of subjects in any group (4 patients) experience an unanticipated serious adverse event (as defined in section 8.1 of IND protocol).

If the study is stopped for any of the reasons listed above, a root cause analysis will be performed to determine cause of adverse event and relationship to study protocol. The study team will formulate an appropriate plan of action to ensure patient safety. Such a plan may include, but is not limited to, protocol modifications, immediate termination of accrual, and adjustments in management of previously enrolled participants continuing to undergo study interventions.

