4.4 Early Withdrawal of Subjects

4.4.1 When and How to Withdraw Subjects

If the patient is unable to comply with the study protocol or they wish to withdraw from the study their participation in the study will be terminated. If the interscalene nerve block catheter becomes occluded or is pulled out prematurely, patients will remain in the study as our primary analysis will be performed based on the intention to treat.

In order to account for 10% dropout, which includes patients terminated from the study, a total sample-size of N=129 (43 per group) is proposed. Follow-up will not be performed for patients terminated from the study due to voluntary purposes.

If the patient chooses not to participate he or she will be provided the current perioperative care plan in place by the surgeon and will include pain management regardless of participation.

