5.3 Method for Assigning Subjects to Treatment Groups

The treatment allocation will be performed using a randomization schedule which will be created by the Division of Biomedical Statistics and Informatics. This randomization schedule will be generated using a SAS program (SAS version 9.3, SAS Institute Inc, Cary NC) with randomization performed in blocks of size N=6 to ensure that after every sixth patient is enrolled there are an equal number of patients assigned to each of the 3 treatment conditions. Using this randomization schedule, an EXCEL spreadsheet application will be created which will include sequentially assigned subject-ID numbers and corresponding treatment assignments. When a patient is enrolled they will be assigned the next sequential subject-ID number and a member of the anesthesia clinical research unit, who will be different from the care team and are not involved in the medical management of the patient, will use the online system to retrieve the allocated treatment assignment for this subject-ID.

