7.1 Sample Size Determination

The sample-size for this study was determined in order to provide statistical power of >90% to detect a difference of 3 units for the primary endpoint (OBAS on POD1). Based on a previous study, we hypothesize that the standard deviation of OBAS will be approximately 3 units.⁴⁴ Under this assumption, an effective sample-size of N=39 per group will provide statistical power of >90% to detect a difference between groups of 3 units using a two-sided, alpha=0.017 (multiple-comparison adjusted for 3 groups), non-parametric test. In addition, for the key secondary endpoint of pain (NRS), this sample-size will provide statistical power of 80% to detect a difference of 0.75 standard deviations (approximately 2.25 units on the NRS). In order to accommodate attrition of approximately 10% (due to canceled surgery, failed block, etc.) we propose a total sample-size of N=129 (43 patients per group).

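### Section 8.5 equates 5% of a group with 4 patients, but with 43 per group 5% is first reached at 3 patients (6.98%) and 4 patients is 9.30%

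*Combined protocol and SAP*

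**What the plan says.** Section 8.5 lists four rules that use a 5% limit. Three of them print no patient count: two for the interscalene arms (block complications; local anaesthetic systemic toxicity) and one for the infiltration arm (systemic toxicity). The fourth covers all three arms and does print one: "The study will stop if 5% of subjects in any group (4 patients) experience an unanticipated serious adverse event".

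The group size is given twice. Section 4.4.1 says "a total sample-size of N=129 (43 per group) is proposed", and section 7.1 says "we propose a total sample-size of N=129 (43 patients per group". Section 7.1 also gives a post-attrition size: "an effective sample-size of N=39 per group will provide statistical power of >90" per cent. Section 5.3 has "randomization performed in blocks of size N=6", so arms may differ slightly when enrolment ends at 129.

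On consequences, section 8.5 says "If the study is stopped for any of the reasons listed above, a root cause analysis will be performed", followed by a plan of action that can extend to ending accrual. It does not say whether the 5% is taken of planned patients or of those enrolled so far.

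**The concern.** One trigger is expressed in two ways that should be equivalent, and at the planned arm size they are not. A stopping rule has to be usable without interpretation, and a team applying this one would probably work from the concrete count. Measured against 43 per arm, that team would carry on with three affected patients, a rate of 6.98%, although the same sentence sets the limit at 5%. This is the only stopping rule for unanticipated serious events. Section 8.5 has the study team do the monitoring and names no independent body to decide which of the two figures governs.

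**Working it through.** **Inputs.** Limit 5% and count 4 (section 8.5); 43 per group and 129 in total (sections 4.4.1 and 7.1); 39 per group after attrition (section 7.1); block size 6 (section 5.3).

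**Attempt to reproduce the printed count.** The required count is the smallest whole number k with k/n ≥ 0.05.

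| Denominator n | 0.05 × n | First k reaching 5% | 4/n |
|---|---|---|---|
| 43 (planned arm) | 2.15 | 3 (6.98%; 2 is 4.65%) | 9.30% |
| 39 (effective arm) | 1.95 | 2 (5.13%) | 10.26% |
| 42 (smallest possible arm) | 2.10 | 3 (7.14%; 2 is 4.76%) | 9.52% |
| 44 (largest possible arm) | 2.20 | 3 (6.82%; 2 is 4.55%) | 9.09% |
| 129 (whole trial) | 6.45 | 7 (5.43%) | 3.10% |

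The range 42 to 44 arises because 129/6 = 21.5: 21 complete blocks give 42 per arm, and the three patients in the last half-block add 0, 1 or 2 to any arm.

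Four is exactly 5% only when n = 4/0.05 = 80. It is the first count to reach 5% for n from 61 to 80. No arm is that large, so four cannot be the first trigger on a running denominator either. Pooling two arms comes close (4/86 = 4.65%; 4/78 = 5.13%), but the rule is written for any single group.

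**Where the two thresholds disagree.** At n = 43, two or fewer events meet neither threshold and four or more meet both. Only exactly three separates them.

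**How often that matters.** Let X be the number of affected patients in a full arm, X ~ Binomial(43, p). The plan gives no value of p, so the rates below are assumptions.

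| Assumed p | P(X ≥ 3) | P(X ≥ 4) | P(X = 3) |
|---|---|---|---|
| 0.5% | 0.13% | 0.01% | 0.13% |
| 1% | 0.9% | 0.1% | 0.8% |
| 2% | 5.5% | 1.1% | 4.4% |
| 5% | 36% | 17% | 20% |

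The rule applies to any group. With the same p in each of three independent full arms, the chance that at least one reaches the trigger is 1 − (1 − P)³:

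- p = 1%: 1 − (1 − 0.0092)³ = 2.7% for three events, against 1 − (1 − 0.0009)³ = 0.3% for four.
- p = 2%: 1 − (1 − 0.0546)³ = 15.5% for three, against 1 − (1 − 0.0106)³ = 3.2% for four.

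**The case against.** The arithmetic is not in dispute. The best case against the point is that it is close to clerical. The conflict needs three unanticipated serious events in one arm of 43, and section 8.5 treats even the known serious events as uncommon: "We acknowledge that despite the rarity of these serious adverse events, the potential still exists". The larger contrast, 36% against 17%, needs a 5% true rate that nothing in the plan supports.

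Other safeguards would probably bring three such events to attention. Section 8.3.1 provides for IRB reporting, though "only directly related SAEs/UPIRTSOs will be reported to the IRB". Where IND rules apply and causality is suspected, section 8.3.2 sets 7- and 15-day FDA reports. Section 8.2 has adverse events sought at daily inpatient encounters, section 3.4 has the principal investigator or a co-investigator told of unanticipated ICU admissions, and section 8.6 requires regular assessment of serious events. The trial is also unblinded, so events are visible by arm.

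These arguments limit the practical effect, and to that extent they stand. They do not make the sentence consistent or tell the team which figure to follow.

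A second objection is that printing three of 43 presumes a planned denominator that the plan never states. That also stands. On accrued patients, one in the first 20 is already 5%, and a fixed count of three would act later than the percentage. The remedy must therefore depend on what the sponsor meant. Measured against the effective 39, the disagreement widens to two or three events, which puts the printed count further out.

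**Conclusion.** The concern holds and should be fixed. The bracketed count is wrong for every per-group size in the document. At the planned 43 it corresponds to 9.30%, nearly double the stated 5%, and the count that matches is three. This reads the rule as at or above 5% of the planned arm.

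The reach is limited. The error sits in one bracket; the other three 5% rules print no count and contain no arithmetic error. At assumed true rates of 1% or below the choice between three and four seldom changes the outcome, and it becomes material only at higher rates. A stop leads to a review and a plan, not automatically to termination. The case for correcting it is that it is a decision threshold in a safety rule.

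**What to change.** Amend only the unanticipated-event rule in section 8.5, choosing by intent:

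- **5% of the planned arm:** replace the bracketed count with 3 of the planned 43 patients. The cost is a slightly higher chance of a pause when the true rate is low: per arm 0.9% instead of 0.1% at an assumed 1%, and 5.5% instead of 1.1% at 2%.
- **Four patients:** keep the count and restate the percentage as about 9%. The cost is a less sensitive trigger: 17% instead of 36% per arm at an assumed 5%.
- **5% of patients accrued so far:** delete the count, because no fixed number matches a growing denominator.

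This correction leaves the other three rules as written; whether their denominator is planned or accrued patients is for the sponsor to state. Any of the options is a short protocol amendment with no added patients or procedures.
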